## 6 Milestones

Planned duration of enrolment period is 70 months.

Milestone	Planned date
Start of data collection Defined as first entry of patient data	01-Jun-2014
Progress report	01-Jun-2016
Interim report	01-Nov-2016  Q4/2018
End of study Defined as Last Patient Last Visit (LPLV)	Q2/2021
End of data collection	Q2/2021
Final report of study results	Q4/2021

The planned duration of this study is 7 years. The study will be concluded when at least 50 patients in the study have reached a minimum 100 exposure days (EDs) after inclusion in the study.

This study is subject to registration no longer than 21 days after enrolment of the first study participant according to Novo Nordisk requirement on non-interventional study disclosure. For countries outside the US, only the main study site per country will be disclosed via facility name, city and country on the study registration. In the US, all study sites will be registered.

The study information is made available in the EU Electronic Register of Post-Authorisation Studies (EU PAS Register) maintained by the European Medicines Agency (EMA) and accessible through the European medicines web portal. The EU PAS Register is currently and temporarily hosted on the ENCePP website <http://encepp.eu/>.

Note: Study registration is regarded as the publication of an internationally agreed set of information (which can be found at the World Health Organisation (WHO) homepage) about the design, conduct and administration of clinical trials. These details are published on a publicly accessible website managed by a registry conforming to WHO standards (also found at the WHO homepage), e.g. [www.ClinicalTrials.gov](http://www.ClinicalTrials.gov).

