### 7.2 Rationale

This protocol describes a non-interventional post authorisation safety study (PASS) of recombinant human coagulation factor VIII (rFVIII).

The major concern in the treatment of haemophilia A is the development of inhibitors against FVIII. The presence of inhibitors neutralizes the effect of FVIII replacement therapy, resulting in increased risk of severe bleeding and development of debilitating haemophilic arthropathy and muscular atrophies, with severe consequences on quality-of-life for the patient.

The risk of developing inhibitors against FVIII is related to the mutation type in the FVIII gene, and possibly to other both genetic and non-genetic factors such as immunoregulatory genes, HLA-type, intensity of treatment, vaccinations or other challenges to the immune system. Inhibitor development in haemophilia A in most cases occurs during the early phases of replacement therapy, usually during the first 50 EDs. The risk of developing inhibitors against FVIII in previously

untreated patients is related to the mutation type in the FVIII gene, and possibly to other both genetic and non-genetic factors such as immunoregulatory genes, HLA type, intensity of treatment, vaccinations or other challenges to the immune system. In previously treated patients, inhibitors develop rarely, with an incidence of an approximate rate of 3 per 1000 patient years. Switching to another FVIII product has not been shown to be associated with increased incidence of inhibitor development. When inhibitors have been detected following switching, time and number of EDs between switching and detection varied considerably, providing no clear indication that inhibitors are more likely to develop in the initial period after switching.

Novo Nordisk has developed turoctocog alfa, a B-domain truncated human recombinant FVIII for use in patients with haemophilia A. The First Human Dose and PK trial (NN7008-3522) comparing turoctocog alfa and Advate® has been completed. The data from the 23 patients showed mean PK profiles of turoctocog alfa comparable to Advate® within the defined limits of comparability.

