Clinical experience included in the marketing application comprises phase 3 results from the pivotal (guardianTM1 - NN7008-3543) and paediatric trials (guardianTM3 - NN7008-3545) in patients with severe haemophilia A (FVIII < 1 %). In the guardianTM1 (NN7008-3543) trial, 146 adult and adolescent patients (>12 years of age) were followed during 75 EDs of preventive dosing with turoctocog alfa either 3 times weekly or every second day. Efficacy in bleeding prevention was demonstrated by a bleeding frequency clearly within the range expected during prophylaxis treatment in haemophilia A (mean annualised bleeding rate of 6.5 bleeds/year). Spontaneous and traumatic bleeds during the trial were treated with a mean dose of 30.4 IU/kg BW (mean total dose used was 45.6 IU/kg BW until stop of bleed), and using a predefined four-point scale (Excellent, Good, Moderate or None) the haemostatic effect of turoctocog alfa was rated as excellent or good in 81 % of all bleeds.

In the paediatric guardianTM3 (NN7008-3545) trial, 63 previously treated patients <12 years of age (<6 years n=31; n=32 6-11 years of age) were dosed with turoctocog alfa and 60 patients completed 50 preventive EDs using a regimen similar to that in the adult/adolescent trial. The bleeding frequency was low with a mean annualised bleeding rate of 5.3 bleeds/year using a mean preventive dose of 36.8 IU/kg BW. Emergent bleeds in the trial were treated with a mean dose of 40.4 IU/kg BW (mean total dose of 50.2 IU/kg BW per bleed) and the haemostatic efficacy was rated as excellent or good in 92.1 % of all bleeds. The number of infusions required to control a bleed was 1-2 in >95 % of bleeds.

After completion of the guardianTM1 (NN7008-3543) and guardianTM3 (NN7008-3545) trials, the vast majority of patients have continued treatment with turoctocog alfa within the extension trial guardianTM2 (NN7008-3568). A 4th Interim analysis of the guardianTM2 (NN7008-3568) trial with a cut-off date 25 March 2015 included 123 patients who have been on prophylaxis with turoctocog alfa for  $\geq$ 36 months. In the entire guardianTM clinical trial programme, 242 previously treated patients

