have been exposed to turoctocog alfa for >50 EDs, and the total exposure now exceeds 100,000 EDs. Despite regular testing and monitoring, no confirmed FVIII inhibitor or other safety concerns have yet been detected within the trials in previously treated patients.

In the recently revised guideline for FVIII products, European Medicines Agency (EMA) points to the importance of ensuring consistency between the outcome from pre-authorisation clinical studies and from long-term routine use, thus mandating a post-marketing investigation if the development program does not include enough EDs. This is also in view of the limited availability of patients suffering from haemophilia A. The present guardianTM5 study (NN7008-3553) is designed to provide additional documentation of the immunogenicity and clinical efficacy of turoctocog alfa.

The U.S. Food and Drug Administration (FDA) have approved Novo Nordisk A/S Biologics License Application (BLA) for turoctocog alfa on the 16th October 2013. Additionally, on the 20th September 2013 the European Medicines Agency's Committee for Medicinal Products for Human Use issued a positive opinion on turoctocog alfa.

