### 9.1 Study design

#### 9.1.1 Type of study

This is a prospective, multinational, non-randomised, non-interventional post-authorisation safety study (PASS) in previously FVIII treated (>150 EDs) patients with severe and moderately severe haemophilia A with FVIII  $\leq 2\%$ . Only patients for whom it has already been decided to start treatment or have already started treatment with commercially available turoctocog alfa and who has not previously participated in any guardianTM clinical trials will be eligible for the study.

Patients with FVIII between 1 and 2% are classified as moderately severe haemophilia A, but most often require treatment due to bleeding tendency. Inclusion of these patients in the present study is in accordance with the EMA guideline for a post marketing investigation for FVIII products, and this patient group is also part of the population intended for treatment with turoctocog alfa. This study will observe at least 50 patients for a minimum of 100 EDs to study product after inclusion in the study. The study duration is estimated to 7 years with a planned recruitment period of 70 months. For each patient, data will be collected in this study:

- until they reach a minimum of 100\* EDs with turoctocog alfa after inclusion in the study **or**
- until at least 50 patients have a minimum of 100\* EDs with turoctocog alfa after inclusion in the study

whichever comes first.

\*the 100 EDs will count from the baseline visit (visit 1)

One exposure day (ED) is defined as each day a patient is administered turoctocog alfa and a 'day' is implicit a 'calendar day'.

E.g. a dosing with turoctocog alfa on 15 June 2015 at 22.30 and a new dose two hours later on 16-Jun-2015 at 00.30 counted as two exposure days.

Several doses with turoctocog alfa within the same calendar day should only be calculated as one exposure day.

Recruitment of patients will aim at a balanced age distribution with at least 20 % of patients being <12 years of age to accommodate for the requirements in the present version of the EMA guideline for factor VIII products, as described in section 9.5. This study will follow routine use of turoctocog alfa in a population with severe and moderately severe haemophilia A FVIII  $\leq 2\%$ . All relevant data recorded by the site during a patient's participation in the study will be captured in the paper Case Report Form (pCRF).

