### **9.1.3 Treatment of patients**

Patients will be treated with commercially available turoctocog alfa as prescribed by the treating Physician in clinical daily practice and preferably according to the label for turoctocog alfa (US PI, European SmPC, or corresponding local prescribing information) in the respective countries. Thus, patients on prophylactic as well as on-demand treatment with turoctocog alfa can be included in the study. Patients undergoing surgical procedures during the study will receive turoctocog alfa bleeding preventive treatment before, during and after surgery according to the label for turoctocog alfa in the respective countries and standard of practice of the participating centre.

Patients who develop inhibitors can continue treatment with turoctocog alfa. If this is decided, the dosing and dosing frequency will be decided by the treating Physician based on the clinical evaluation, see [Figure 9-1](#).

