## **9.2 Setting**

### **9.2.1 Number of patients to be studied**

The below listed numbers represent the sum of patients participating:

Planned number of patients to be included (baseline screening):	Approx. 80
Planned number of patients to be included in the study:	Approx. 70
Planned number of patients to complete the study:	Approx. 50
Anticipated number of patients to be included in each country:	Approx. 5-8

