### **9.7.3 Primary endpoint**

The incidence rate of inhibitors ( $\geq 0.6$  BU for central laboratory analyses, or above the specific local laboratory reference range) represented as the percentage of patients developing inhibitors will be calculated and a 1-sided 97.5% upper confidence limit will be provided based on an exact calculation for a binomial distribution. For the calculation of the incidence rate the numerator will include all patients with inhibitors confirmed by laboratory except those patients who have received a positive inhibitor test result after inclusion in the study for a test performed prior to first dose of turoctocog alfa. The denominator will include all patients in the trial exposed to turoctocog alfa,

except those patients who have received a positive inhibitor test result after inclusion in the study for a test performed prior to first dose of turoctocog alfa, these patients will be listed separately.

In addition, the time to inhibitor development will be presented by Kaplan Meier plot. Furthermore, an annualised rate of inhibitors per patient year will be calculated using a Poisson model allowing for over-dispersion with a log-link function and the logarithm of the time spent in the trial as offset, if appropriate.

Analyses and presentations will be made for each treatment regimen (preventive treatment or on-demand treatment) and for all patients, and furthermore for each patient subgroup (Severity of Haemophilia A: severe, moderately severe or patients with surgery/invasive procedure).

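### The over-dispersed Poisson model named for the supplementary inhibitor rate per patient-year is unsuited to the likeliest result, zero inhibitors, and no alternative is named

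*Protocol*

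**What the plan says.** Protocol section 9.7.3 gives the inhibitor result in three forms. The first is the primary percentage of patients with an inhibitor, with a 1-sided 97.5% upper limit from an exact binomial calculation. The second is a Kaplan-Meier plot. The third is a rate over time: "an annualised rate of inhibitors per patient year will be calculated using a Poisson model allowing for over-dispersion". This model has a log link and the logarithm of time spent in the trial as offset, and the sentence closes by making it conditional on being appropriate. The section does not say when the model would be inappropriate, what would replace it, or whether the rate has a confidence limit. It asks for the analyses by regimen, for all patients and by subgroup. Section 9.7.2 adds two interim data cuts covering all endpoints.

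On the expected number of events, section 7.2 says that in previously treated patients "inhibitors develop rarely, with an incidence of an approximate rate of 3 per 1000 patient years". For this product it adds that "no confirmed FVIII inhibitor or other safety concerns have yet been detected within the trials in previously treated patients". On what happens after an inhibitor, section 9.1.3 says: "Patients who develop inhibitors can continue treatment with turoctocog alfa".

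**The concern.** A log-link Poisson model with an estimated dispersion needs events. If none occur, the log rate has no finite value, and neither the dispersion nor the standard error can be estimated. The protocol's own background figures make none the likeliest count. The same holds more strongly in the regimen and severity subgroups and at the interim cuts, where person-time is smaller.

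The dispersion term is also a poor match for the endpoint. Each patient counts at most once as having developed an inhibitor, so there is no within-patient clustering of events for it to describe. The offset is all time in the trial, although a patient who already has an inhibitor may stay and is no longer at risk of a first one.

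At stake is a supplementary descriptive figure. If the model fails, the rate is either dropped or produced by a method chosen after the data are seen.

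**Working it through.** The protocol states no expected count or precision for this rate, so there is no figure to reproduce.

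**Inputs**
- Background rate: 3 per 1000 patient-years (section 7.2).
- Completers: "This study will observe at least 50 patients for a minimum of 100 EDs to study product after inclusion in the study" (section 9.1.1).
- Section 9.2.1, "Planned number of patients to be included in the study": about 70.
- EDs per week: not given, because regimens follow routine practice. Assumed 3 to 3.5, from the earlier pivotal trial's dosing, "either 3 times weekly or every second day" (section 7.2). Slower accrual, down to 1 per week, is shown because on-demand patients are eligible.

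**Step 1: chance of zero events**

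Patient-years (PY) = n × 100 / (EDs per week) / 52.18. Expected events m = 0.003 × PY. P(0) = exp(−m). The exact 1-sided 97.5% upper limit at zero events is χ²(0.975; 2 df)/2 ÷ PY = 3.689/PY.

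| n | EDs/week | PY | m | P(0) | Upper limit at 0 events, per 1000 PY |
|---|---|---|---|---|---|
| 50 | 3.5 | 27.4 | 0.082 | 0.92 | 135 |
| 50 | 3 | 31.9 | 0.096 | 0.91 | 115 |
| 50 | 1 | 95.8 | 0.287 | 0.75 | 38 |
| 70 | 3.5 | 38.3 | 0.115 | 0.89 | 96 |
| 70 | 3 | 44.7 | 0.134 | 0.87 | 82 |
| 70 | 1 | 134.2 | 0.402 | 0.67 | 27 |

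Zero is the most likely count in every row. Section 6 says "The planned duration of this study is 7 years". Even an unrealistic 50 patients each followed for all 7 years (350 PY) would give m = 1.05 and P(0) = 0.35.

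**Step 2: the model at zero events**

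An intercept-only Poisson model with log link, log-time offset and Pearson-scaled dispersion was fitted to 70 patients with no events. The fit stopped with a boundary error: the intercept goes to minus infinity, and the dispersion and Wald standard error are undefined.

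**Step 3: the model at one event**

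Let total time be T, and let the patient with the inhibitor have follow-up t. The fitted rate is 1/T and each fitted mean is (own time)/T. The Pearson statistic reduces to T/t − 1, so the dispersion is

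φ = (T/t − 1)/(n − 1).

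The 95% interval is (1/T) × exp(±1.96√φ). With n = 70 and T = 38.3 the rate is always 26 per 1000 PY, but the interval is not fixed. The values of t are illustrative:

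| Follow-up of the patient with the inhibitor | φ | 95% interval, per 1000 PY |
|---|---|---|
| 0.20 years | (191.5 − 1)/69 = 2.76 | 1.0 to 678 |
| 0.547 years (the mean) | (70 − 1)/69 = 1.00 | 3.7 to 185 |
| 0.85 years | (45.06 − 1)/69 = 0.64 | 5.5 to 125 |
| Exact Poisson, any patient | none | 0.66 to 145 |

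The exact row is 0.0253/38.3 and 5.572/38.3. Direct fits of the model gave the same φ and intervals. With one event, the dispersion therefore measures only how long that patient was followed relative to the others.

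**Step 4: the primary percentage at zero events**

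The upper limit is 1 − 0.025^(1/n): 7.1% for 0/50 and 5.1% for 0/70. It is computable and unaffected.

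**The case against.** The strongest reply is that the model is conditional. The protocol does not commit to fitting it where it cannot be fitted, and a rule for sparse events is ordinary content for a statistical analysis plan, which is not at hand. This stands in part. The protocol is not silent, however: it names a specific model, that model is unsuitable for the likeliest result, and the qualifier gives neither a condition nor an alternative.

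A reader might infer that the rate will have no estimate at all. The documents do not support that. At zero events the crude rate is simply 0, and section 9.7.3 promises a limit only for the percentage, so no promised limit is lost.

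A reader might also infer that a planned comparison with 3 per 1000 patient-years fails. That figure is background in section 7.2, and nowhere is it made a comparator. Under the assumed 3 to 3.5 EDs per week, the exact upper limits at zero events are 82 to 135 per 1000 patient-years, so the study could say little against 3 by any method. Section 9.7.4 also plans adverse reaction rates per 100 patient-years, so events and person-time will be available.

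The offset point has almost no numerical weight. With no events it changes nothing. With one inhibitor among 70 similarly followed patients, the miscounted time is at most about 1/70, or 1.4%, of the total. Nor is the model's upper limit always too low: at average follow-up it is 185, against 145 exact.

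**Conclusion.** The point holds as a minor one. Section 9.7.3 names a model that cannot be fitted on the log scale at zero inhibitors. At the protocol's background rate that outcome has probability 0.87 to 0.92 under 3 to 3.5 EDs per week, and 0.67 to 0.75 at 1 per week. At one inhibitor its interval depends on whose inhibitor it was. These probabilities rest on the assumed accrual speed, on 50 to 70 patients each contributing 100 EDs, and on the background rate applying to this population.

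The stronger reading, that the study's main inhibitor result is at risk, is not supported. The primary endpoint is the percentage, its exact binomial limit works at zero, no hypothesis is tested (section 9.7.1), and the modelled rate is a conditional addition.

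**What to change.** In section 9.7.3, replace the Poisson model with the number of patients with a confirmed inhibitor divided by total person-time, with an exact Poisson 1-sided 97.5% upper limit to match the percentage. At zero events this limit is 3.689 divided by patient-years, for example about 96 per 1000 at 38.3 patient-years. State that a patient's person-time ends at inhibitor development. Use the same calculation for each regimen, each subgroup and each interim cut, and drop the qualifier, since the exact limit exists at any count.

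A rate per 1000 EDs could be added, because on-demand and preventive patients accrue EDs at different speeds, but this is optional.

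The cost is one sentence and simpler programming. No new data are needed and the primary analysis does not change.

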#### **9.7.4 Secondary endpoints**

##### **Safety endpoints**

- Number of adverse reactions (ARs) reported during the study period
- Number of serious adverse reactions (SARs) reported during the study period

ARs and SARs reported during the study will be summarised by number of reactions and number of patients with any reaction. Since patients will have different durations in the study adverse reaction rates (reactions per 100 patient years of exposure) will also be calculated and presented. Similar summaries cross-classified by severity will also be made. The summary tables will be made by type of regimen.

Furthermore, listings will be provided displaying all ARs and SARs reported during the study including pertinent clinical information.

##### **Efficacy endpoints**

- Haemostatic effect of turoctocog alfa in the treatment of bleeds as assessed by the patient or the Physician according to a predefined four point scale: Excellent, Good, Moderate, or None

This endpoint will be summarised and listed. In addition treatment success will be summarised by counting Good or Excellent as success and None and Moderate as failure. Missing will be excluded since reporting the endpoint is optional.

- Haemostatic effect of turoctocog alfa during surgical procedures as assessed by evaluation according to a predefined four point scale: Excellent, Good, Moderate, or None

This endpoint will be summarised and listed. In addition treatment success will be summarised by counting Good or Excellent as success and None, Moderate as failure. Missing will be excluded since reporting the endpoint is optional. Annualised bleeding rate for patients using turoctocog alfa for preventive treatment

- Annualised bleeding rate for patients using turoctocog alfa for on-demand treatment

The annualised bleeding rate will be analysed by a negative binomial model and estimated annualised bleeding rate with confidence interval will be presented. As a sensitivity analysis, a Poisson model with over-dispersion will also be applied.

- Total consumption of turoctocog alfa per patient (prevention, treatment of bleeds and surgery) per month

This endpoint will be summarised and listed.

- Actual consumption of turoctocog alfa (IU/kg BW/months) for prevention

This endpoint will be summarised and listed.

- Actual consumption of turoctocog alfa per bleed (IU/kg BW/bleeding episode)

This endpoint will be summarised and listed.

- Actual consumption of turoctocog alfa (IU/kg BW) from the day of surgery until the day of return to preventive regimen

This endpoint will be summarised and listed.

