**For surgery, the following data should be recorded in the patient's record and the pCRF, if available:**

- Type of surgery (planned or emergency)
- Surgery intervention:
  - Surgical procedure and indication
  - Clinical evaluation of haemostatic response during surgery (Excellent, Good, Moderate, or None)
- Date of surgery
- Study product doses in relation to peri-operative period (surgery day and post-surgical recovery period)
- FVIII inhibitor tests on the day of surgery and a second test in the interval 10 - 14 days post-surgery
- Clinical narrative of the procedure

Treatment and study assessments to be made in an emergency situation are at the discretion of the Physician. If a patient change his regular treatment to another FVIII products other than turoctocog alfa after initiation of study product treatment within this study the patient must be withdrawn from the study in accordance with withdrawal criteria no. 4, please see section [9.2.4](#).

For additional information, please see section [9.3.2.4](#).

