**For bleeds the following should be recorded in patient's diary and pCRF:**

- Date and time of onset of bleeding episode
- Treatment of bleeding episode
- Location of the bleed (specify location e.g. joint, muscular etc.)
- Type of bleed (spontaneous, traumatic)
- Haemostatic drug used for treatment
- Dose level(s), strength(s) and time(s) of administration
- Other therapy used (compression, ice or other)
- Date and time of stop of bleeding episode
- Severity of the bleed (Mild/Moderate or Severe)
- Clinical evaluation of the haemostatic response (Excellent, Good, Moderate or None)

A need for haemostatic rescue therapy with another FVIII product will be assessed by the Physician via phone or during a site visit. Patients treated with FVIII products other than study product during the time of their participation in this study must be withdrawn from the study, see section [9.2.4](#).

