### **9.3.4.9 Diary**

Diaries will be used in this study. The patient should be asked to bring the diary(ies) to every visit to the site.

The following data should be captured by the patient and/or parent:

- Treatment
  - FVIII product used
  - Prophylaxis treatment
  - Every single dose level and strength
  - Date and time of dose administration
- Bleeds
  - Date and time of onset of bleeding episode
  - Treatment of bleeding episode
  - Location of the bleed (specify location e.g. joint, muscular etc.)
  - Type of bleed (spontaneous, traumatic)
  - Haemostatic drug used for treatment
  - Every single dose level(s), strength(s) and time(s) of administration
  - Other therapy used (compression, ice or other)
  - Date and time of stop of bleeding episode
  - Severity of the bleed (Mild/Moderate or Severe)
  - Clinical evaluation of the haemostatic response (Excellent, Good, Moderate or None)

The Physician should carefully instruct the patient in how to evaluate a bleed, the haemostatic response after treatment and how to complete the diary. The Physician is recommended to retrain the patient, if needed.

Entries made in the diary should preferably be reviewed by the Physician together with the patient/caregiver at each visit to the clinic; and should be entered in the pCRF by the site staff. The information in the patient's diary is regarded as source data. If information missing in the diary is available in the medical records, this information can be used.

In case study product administration is performed at the site, this should be entered in the medical record and subsequently in the pCRF for the respective assessment visit, by the Physician. The study product must not be reported in the diary when the administration is performed at the site.

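### Unrated bleeds and surgeries are left out of the haemostatic success rate on the ground that rating is optional, although for bleeds the protocol asks for a rating every time; the rate may be overstated and no bound is planned.

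*Protocol*

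**What the plan says.** Section 9.7.4 (Efficacy endpoints) summarises and lists the four-point haemostatic rating. It then adds a two-category summary for bleeds: "treatment success will be summarised by counting Good or Excellent as success and None and Moderate as failure". Surgery is handled the same way. Under each endpoint the rule for absent ratings is: "Missing will be excluded since reporting the endpoint is optional".

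The data-collection sections treat the two ratings differently.

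- **Bleeds, section 9.3.2.1.** The list opens with "For bleeds the following should be recorded in patient's diary and pCRF" and includes "Clinical evaluation of the haemostatic response (Excellent, Good, Moderate or None".
- **Bleeds, section 9.3.4.9.** The same item appears in the diary list, introduced by "The following data should be captured by the patient and/or parent". No qualifier is attached, and the Physician is told to train the patient in judging the response.
- **Surgery, section 9.3.1.2.** The list that contains the response during surgery opens with "For surgery, the following data should be recorded in the patient's record and the pCRF, if available".

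Both ratings are among the key secondary endpoints in the abstract. The protocol names no other handling of missing ratings. By contrast, the annualised bleeding rate in section 9.7.4 has a named sensitivity analysis.

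**The concern.** The denominator of the success rate is the set of episodes that someone rated, not the set that was treated. If unrated episodes fared worse than rated ones, the reported percentage is too high, and nothing planned for that percentage would show by how much.

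The protocol contains routes by which this could happen. Bleeds treated in hospital, or when the patient cannot write, bypass the diary and rely on later entry by the Physician (sections 9.3.2.1 and 9.3.2.2). Section 9.3.2.1 also says: "Patients treated with FVIII products other than study product during the time of their participation in this study must be withdrawn from the study". A poor response could thus coincide with the end of diary keeping.

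The stated reason matters too. If a rating is expected for each treated bleed, its absence is missing data that needs handling, not an allowed omission that can be set aside.

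**Working it through.** **The reason set against data collection**

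| Rating | Collection instruction | Reason in 9.7.4 | Consistent? |
|---|---|---|---|
| Bleeds | Should be recorded or captured, unqualified (9.3.2.1, 9.3.4.9) | Optional | No |
| Surgery | Only if available (9.3.1.2) | Optional | Yes |

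The conflict is therefore confined to bleeds. The rated-only denominator applies to both.

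**How far the rate can move**

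The protocol states no target, expected rate or missing share for this endpoint, so there is no planned figure to reproduce. Bounds follow directly.

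Inputs:
- s = success among rated episodes. For illustration only, s = 81% and s = 92.1%, the rates that section 7.2 quotes from the adult/adolescent and paediatric trials.
- m = share of episodes unrated. This is assumed at 10%, 20% and 30%.

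Formulas:
- Reported under the protocol's rule: s
- All unrated episodes failed: s(1 − m)
- All unrated episodes succeeded: s(1 − m) + m
- Largest overstatement: s − s(1 − m) = s·m
- Largest understatement: s(1 − m) + m − s = (1 − s)·m

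| m (assumed) | Range if 81% reported | Range if 92.1% reported |
|---|---|---|
| 10% | 72.9% to 82.9% | 82.9% to 92.9% |
| 20% | 64.8% to 84.8% | 73.7% to 93.7% |
| 30% | 56.7% to 86.7% | 64.5% to 94.5% |

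At m = 20%:
- s = 81%: overstated by at most 0.81 × 0.20 = 16.2 points, understated by at most 0.19 × 0.20 = 3.8 points.
- s = 92.1%: overstated by at most 0.921 × 0.20 = 18.4 points, understated by at most 0.079 × 0.20 = 1.6 points.

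An intermediate case, again assumed: if half of the unrated bleeds succeeded, the all-bleeds rates would be 0.648 + 0.20 × 0.5 = 74.8% and 0.7368 + 0.20 × 0.5 = 83.7%. If unrated bleeds succeed at the same rate as rated ones, there is no bias.

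**Surgery**

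With few procedures the effect is coarse. Suppose 10 surgeries, 2 unrated and the other 8 successful. The protocol's rule reports 8/8 = 100%; counting missing as failure gives 8/10 = 80%.

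**The case against.** The strongest reply is that no upward bias has been shown. A reader might infer from the exclusion rule that success is likely overstated. The documents do not support that, for these reasons:

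- They give neither the share of episodes unrated nor the pattern.
- The endpoint is defined as "Haemostatic effect of turoctocog alfa in the treatment of bleeds as assessed by the patient or the Physician", so an incomplete diary need not mean a missing rating.
- The Physician enters episodes the patient could not record, section 9.3.4.9 lets medical records fill diary gaps, and section 9.3.1 asks for last-visit procedures at withdrawal where possible.
- A mild bleed that settles quickly at home may be just as likely to go unrated.

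This stands. The bounds allow more room for overstatement than for understatement, but only because s is high. That is not evidence of direction.

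A reader might also infer that the result cannot be compared with the 81% and 92.1% in section 7.2, which are described there as shares of all bleeds. The protocol plans no such comparison and does not say how those trials handled unrated bleeds, so this is unproven.

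On the wording, the protocol carries general availability qualifiers (section 9.3; Table 9–1, footnote 3; the visit lists in 9.3.1.2 and 9.3.1.3), and should is weaker than must. That softens the conflict for bleeds without removing it, since the two lists that name the rating carry no qualifier. For surgery there is no conflict.

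Finally, it can be said that table layout belongs in the statistical analysis plan, that unrated episodes may be visible in the listings, and that section 9.9 already concedes the limits of routine-practice data. But the protocol does not leave this open: it fixes the exclusion and gives a reason. A listing does not alter the percentage, and section 9.9 does not address selective rating. The further analyses mentioned in section 9.7.5 are discretionary and concern the influence of single patients.

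**Conclusion.** The point holds in a limited form. Section 9.7.4 fixes a rated-only success rate for a key secondary endpoint, and for bleeds its reason conflicts with sections 9.3.2.1 and 9.3.4.9. The reported rate may be overstated, by at most s × m. At an assumed 20% unrated that is 16.2 points on 81% or 18.4 points on 92.1%, against possible understatement of 3.8 or 1.6 points. The missing share is an assumption, the two values of s are borrowed for illustration, and each bound supposes that every unrated episode went the same way. The direction of any actual bias is not known from the documents.

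The analysis is descriptive, with no hypothesis test, and the primary inhibitor result does not depend on it. This is a worthwhile, inexpensive improvement, not a threat to the study's main conclusion.

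**What to change.** In section 9.7.4:

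1. Keep the rated-only success rate.
2. Beside it, add a sensitivity summary over all treated bleeds with missing ratings counted as failure.
3. Do the same over all surgeries, labelled as a lower bound because that rating is collected only when available.
4. Report the number and percentage of unrated episodes by regimen.
5. For bleeds only, reconcile the optional rationale with sections 9.3.2.1 and 9.3.4.9. The surgery rationale can stay.

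The cost is a few extra table rows and no new data collection. The added figure is a deliberately conservative lower bound and may look less favourable than the rated-only rate, so it should be labelled as a bound and not offered as a replacement estimate.
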